### **7.2.2 Analyses of Additional Secondary Endpoints**

For the additional secondary endpoints, binary endpoints and time to event endpoints will be analyzed similarly as for the key secondary endpoints, with the only exception that there will be no hypothesis testing.

For continuous endpoints (length of hospitalization, length of ICU stay, duration of mechanical ventilation), summary statistics by treatment arm will be provided including number of patients, median, mean, standard deviation, minimum, and maximum.

For duration of mechanical ventilation, sensitivity analyses will be performed in the same manner as RMV.

For PaO2:FiO2 and/or oxygenation index over time, only descriptive statistics will be provided.

#### **7.2.2.1 Determination of the anti-inflammatory and immune effect of selinexor**

The following endpoints will be summarized by time. Change from baseline will also be summarized. The analyses will be descriptive only, no hypotheses testing will be performed.

- Reduction of C-reactive protein (CRP)
- Reduction in ferritin levels

- LDH
- Measure changes from baseline of blood plasma cytokines: IL-1 $\beta$ , IL-1R $\alpha$ , IL-2, IL-4, IL-5, IL-6, IL-7, IL-8, IL-9, IL-10, IFN $\gamma$ , IP10, TNF $\alpha$

### **7.3 Analyses of Exploratory Endpoints**

CCI

## **8. SAFETY ANALYSES**

Safety endpoints include AEs, clinical laboratory variables, vital signs, and ECGs.

Unless otherwise specified, all safety analysis will be performed by treatment arm according to the treatment the patient actually received using the AT and POC populations.

### **8.1 Adverse Events**

Adverse events (AEs) will be coded using the most recent version of MedDRA.

The severity of all AEs will be graded according to the NCI CTCAE Grading Scale, v. 5.0. An AE with a CTCAE grade of 3 or higher is considered a severe AE. The severity of the AE is different from the seriousness of the AE. For AEs not covered by CTCAE, the severity will be characterized as “mild,” “moderate,” “severe”, “life-threatening” (corresponding to Grades 1 to 4). Handling rules for missing severity of AEs are described in Section 4.4.3.

Treatment emergent adverse events (TEAEs) are defined as those AEs that develop or worsen after the first dose of study treatment and up to 30 days beyond the last dose of study treatment. Additionally, any AEs that occurred 30 days after the last dose of study treatment will also be considered as TEAE, if assessed by the Investigator as related to study treatment.

AEs are classified as related or not related to study treatment. Any AEs with missing or unknown relationship will be considered as related to study treatment.

All summaries of AEs described in this section will be on TEAEs. All summaries will be ordered by decreasing frequency of total number of patients in overall in PT within SOC which is sorted alphabetically. In the case of equal frequency of number of patients in PTs, then summaries of AEs will be sort alphabetically.

An overall summary for AEs including number of patients who experience an TEAE will be provided:

- TEAEs
- Grade 3/4 TEAEs
- Serious TEAEs
- TEAEs leading to study treatment discontinuation
- TEAEs leading to dose reduction of study treatment
- TEAEs leading to dose interruption of study treatment
- TEAEs leading to death
- Treatment-related TEAEs
- Treatment-related serious TEAEs

- Treatment-related TEAEs leading to study treatment discontinuation
- Treatment-related TEAEs leading to dose reduction of study treatment
- Treatment-related TEAEs leading to dose interruption of study treatment
- Treatment-related TEAEs leading to death

The following types of TEAEs will be summarized by primary SOC and PT:

- All TEAEs
- All TEAEs, by causality
- All TEAEs, by maximum grade
- Grade  $\geq 3$  TEAEs
- Grade  $\geq 3$  TEAEs, by causality
- TEAEs leading to study treatment discontinuation
- TEAEs leading to dose reduction of study treatment
- TEAEs leading to dose interruption of study treatment
- TEAEs leading to death
- Serious TEAEs
- Serious TEAEs, by causality

If a SOC or PT was reported more than once for a patient, the patient would only be counted once in the incidence for that SOC or PT.

For patients experiencing the same PT at multiple severities, the occurrence of the AEs with the greatest severity will be used in the analysis of incidence by severity.

For patients experiencing the same PT at multiple relationship levels, the occurrence of the AEs with the strongest relationship to study treatment will be used in the analysis of incidence by relationship to study treatment.

An overview of all death events and primary cause of death will be provided.

The following listing will be provided:

- All AEs
- Serious AEs
- AEs leading to study treatment discontinuation
- AEs leading to dose modification (reduction, interruption)
- Death

## 8.2 Clinical Laboratory Data

All laboratory parameters will be normalized by converting values in original units to values in SI units and classified as normal, abnormal low, or abnormal high on normal ranges supplied by the local laboratories and upon employing standardization.

Observed and change from baseline of clinical laboratory data (hematology, serum chemistry and coagulation) will be summarized at each analysis visit by treatment arm.

Whenever applicable, severity of selected clinical laboratory measures will be determined based on the CTCAE criteria. Laboratory values with CTCAE Grade  $\geq 3$  will be presented in a data listing. The worst toxicity grade in hematology and chemistry will be summarized by toxicity grade. Shift tables that present changes from baseline to worst on-study relative to CTCAE classification ranges will be presented. These shift tables will include results from unscheduled visits.

### **8.3 Vital Signs**

Observed and change from baseline of vital signs (including temperature, pulse rate, respiratory rate, systolic and diastolic blood pressure, oxygen saturation) will be summarized at each analysis visit by treatment arm, up to ICU admission if applicable.

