**SCHEDULE OF ASSESSMENTS**

**Table 1: Schedule of Assessments for admitted patients only**

| Activity/Assessment                            | Screening  | Dosing Period                     |           |           |           |            |            |             |             |            |            | End-of-Treatment | Hospital Discharge | Safety Follow-Up / End of Study  |
|--|------------|-----------------------------------|-----------|-----------|-----------|------------|------------|-------------|-------------|------------|------------|------------------|--------------------|--|
|  | D -2 to D1 | D1 ±1 day                         | D3 ±1 day | D5 ±1 day | D8 ±1 day | D10 ±1 day | D12 ±1 day | D 15 ±1 day | D 19 ±1 day | D22 ±1 day | D26 ±1 day | D14/28*          |                    |  |
| Informed Consent b                  | X          |                                   |           |           |           |            |            |             |             |            |            |                  |                    |  |
| Inclusion/Exclusion                            | X          |                                   |           |           |           |            |            |             |             |            |            |                  |                    |  |
| Demographics                                   | X          |                                   |           |           |           |            |            |             |             |            |            |                  |                    |  |
| Medical history                                | X          |                                   |           |           |           |            |            |             |             |            |            |                  |                    |  |
| Disease History                                | X          |                                   |           |           |           |            |            |             |             |            |            |                  |                    |  |
| Vital signs c                       | X          | Twice daily during Hospital Stay  |           |           |           |            |            |             |             |            |            |                  |                    |  |

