##### 4.1. Inclusion Criteria

Patients are eligible to be included in the study only if they meet all the following criteria:

1. Age  $\geq 18$  years
2. Confirmed laboratory diagnosis of SARS-CoV2 by standard FDA-approved RT-qPCR assay or equivalent FDA-approved testing (local labs) within 7 days of enrollment.
3. Currently hospitalized.
4. Informed consent.
5. Has symptoms of severe COVID-19 as demonstrated by:
  - a. At least one of the following: fever, cough, sore throat, malaise, headache, muscle pain, shortness of breath at rest or with exertion, confusion, or symptoms of severe lower respiratory symptoms including dyspnea at rest or respiratory distress.
  - b. Clinical signs indicative of lower respiratory infection with COVID-19, with at least one of the following: SaO2  $< 92\%$  on room air in last 12 hours or requires  $\geq 4$  LPM oxygen by nasal canula, non-rebreather/Ventimask (or similar device) or high flow nasal canula in order to maintain SaO2  $\geq 92\%$ , PaO2/FiO2  $< 300$  mm/hg. Patients with COPD or chronic lung disease must demonstrate evidence of increased oxygen needs above baseline.
6. Elevated CRP  $> 2 \times$  ULN
7. Concurrent anti-viral and/or anti-inflammatory agents (e.g., biologics, hydroxychloroquine) are permitted. If in the physician's judgement, it is in the best interest of the patient to use anti-viral or anti-inflammatory treatments, these treatments are to be documented in the patient's chart and entered in the electronic case report form.

Note: Patients who may have received plasma convalescent therapy  $> 48$  hours prior to enrollment with no clinical improvement and who still meet criteria for severe COVID-19 may enroll. On study plasma convalescent therapy is not permitted.

Patient who receive plasma convalescent therapy within 48 hours may be permitted to enroll based on discussion with sponsor.

8. Female patients of childbearing potential must have a negative serum pregnancy test at Screening. Female patients of childbearing potential and fertile male patients must use highly effective methods of contraception throughout the study and for 3 months following the last dose of study treatment. Highly effective methods of contraception are listed in Section 8.3.1.

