##### 4.2. Exclusion Criteria

Patients are excluded from the study if any of the following criteria apply:

1. Evidence of critical COVID-19 based on:
  - a. Respiratory failure (defined by endotracheal intubation and mechanical ventilation, oxygen delivered by noninvasive positive pressure ventilation, or clinical diagnosis of respiratory failure in setting of resource limitations)
  - b. Septic shock (defined by investigator assessment or requires vasopressor)
  - c. Multiple organ dysfunction/failure
2. In the opinion of the investigator, unlikely to survive for at least 48 hours from screening
3. Inadequate hematologic parameters as indicated by the following labs:
  - a. Patients with severe neutropenia ( $ANC < 1000 \times 10^9/L$ ) or
  - b. Thrombocytopenia (e.g., platelets  $< 100,000$  per microliter of blood)
4. Inadequate renal and liver function as indicated by the following labs:
  - a. Creatinine clearance (CrCL)  $< 20$  mL/min using the formula of Cockcroft and Gault.
  - b. Aspartate transaminase (AST) or alanine transaminase (ALT)  $> 5$  x upper limit of normal (ULN)
5. Hyponatremia defined as sodium  $< 130$  mEq/L
6. Unable to take oral medication when informed consent is obtained.
7. Patients with a legal guardian or who are incarcerated.
8. Treatment with strong CYP3A inhibitors or inducers. A list of strong CYP3A inhibitors and inducers is provided in [Appendix 3](#).
9. Pregnant and breastfeeding women.

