#### 5.2.3. Dosing Information

Study treatment tablets should be taken orally with at least 120 mL (4 ounces) of water. Study treatment can be taken with or without food. In order to avoid contact with skin, tablets must be swallowed whole and should not be crushed.

Eligible patients must be able to take oral medication when informed consent is obtained. If a patient is later intubated or unable to take oral medication during treatment, it is permissible to use selinexor suspension prepared as below:

A suspension of selinexor and/or placebo can be prepared by the site pharmacy from selinexor tablets, water, and the commercial suspension agent Ora-Blend®. The pharmacy should place one 20 mg active or placebo tablet in a bottle (amber if available) and add 3 mL of water to disintegrate the tablet, then add 9 mL of Orablend® suspending agent. Gentle swirling or

inversion of the capped bottle will mix the suspension and suspend selinexor for dosing. The resulting suspension should be dosed within 4 hours. Administer the suspension to the patients using an oral dosing syringe via a nasogastric (NG) or percutaneous endoscopic gastrostomy (PEG) feeding tube. Rinse the bottle, syringe and tube with 40 mL to 110 mL of saline and dose the saline rinse to the patient to ensure complete delivery of the selinexor/placebo dose.

Handling Precaution: Selinexor tablets are coated for easy handling. Do not break, cut, or crush selinexor tablets because of increased risk of dermatologic toxicity (e.g., rash) from exposure to the active ingredient in the tablets.

Handling Precaution: The tablets quickly disintegrate in water (<10 min) without being crushed. Please wear gloves when handling the suspension to prevent unintended exposure to the active ingredient. The site pharmacy should consult the pharmacy manual for full instructions on preparing and handling the suspension and for alternative suspending agents should Ora-Blend® be unavailable.

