Day 14 Ordinal Scale 1 point improvement (OSI1-14)	Proportion of patients with at least a 1 point improvement (increase) in the Ordinal Scale from baseline to Day 14. The improvement is assessed the same as in OSI2-14.
Time to an improvement of 1 point on the Ordinal Score (TTCI-1)	The time from randomization to an improvement of 1 point on the Ordinal Scale. For patients who didn't achieve clinical improvement of 1 point, the censoring rule will be the same as that in TTCI-2.
Overall survival (OS)	Time since randomization to death date, or the last contact date with patient status being alive, on or before EoS or database cut date, whichever occurs first.
Overall death rate on Day 14 (DR-14)	Proportion of patients died on or before Day 14.
Rate of ICU admission	Proportion of patients with ICU admission.
Length of hospitalization	Length of hospital stay defined as cumulative length of hospital stay.
Length of ICU stay	Cumulative length of ICU stay.
Duration of mechanical ventilation	Cumulative number of days with invasive mechanical ventilation or ECMO

PaO 2 :FiO 2 and/or oxygenation index over time	PaO 2 :FiO 2 and/or oxygenation index over time. Will be summarized by visit using descriptive statistics.
---	--

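### The only planned vital-sign summaries stop at ICU admission, a post-randomization outcome, so the between-arm tables are selectively truncated

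*SAP*

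**What the plan says.** SAP 8 makes vital signs a safety endpoint: "Safety endpoints include AEs, clinical laboratory variables, vital signs, and ECGs". SAP 8.3 then gives their only analysis. Temperature, pulse, respiratory rate, blood pressure and oxygen saturation, as observed values and changes from baseline, "will be summarized at each analysis visit by treatment arm, up to ICU admission if applicable". The SAP plans no full-period table, shift or worst-value table, abnormality flag or listing for vital signs.

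The protocol's schedule of assessments (Table 1) collects vital signs "Twice daily during Hospital Stay" and does not stop at ICU admission. Protocol 5.2.3 foresees treatment continuing in patients who deteriorate: "If a patient is later intubated or unable to take oral medication during treatment, it is permissible to use selinexor suspension". SAP Table 6 lists the rate of ICU admission as an additional secondary endpoint, "Proportion of patients with ICU admission".

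For laboratory data, SAP 8.2 uses nearly the same by-visit wording without the ICU clause: observed values and changes ("hematology, serum chemistry and coagulation) will be summarized at each analysis visit by treatment arm"). It adds shift tables to the worst on-study value.

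**The concern.** Cutting a safety summary at an event that happens after randomization, and that treatment may influence, means later visits no longer compare the randomized groups. They compare the patients in each arm who have not yet been admitted to ICU. If selinexor raised ICU admission, more of its sickest patients would leave the table. If it lowered admission, the distortion would run the other way. Even with equal admission rates, any treatment effect on vital signs during or after ICU care would go unseen.

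The omitted readings are ones the protocol already collects, and some may be taken on treatment. They also matter clinically: Table 7 in protocol Appendix 2 reports hypotension in 3 of 25 patients (12%) at low doses of selinexor, with onset by Day 14. The SAP gives no reason for treating vital signs differently from its other safety data.

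**Working it through.** The plan states no figure to reproduce and the documents give no ICU rate. The check is therefore a comparison of rules, followed by arithmetic on labelled assumptions.

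**1. Cut-off rules side by side.**

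| Safety data | SAP section | ICU cut-off | Extreme values shown by |
|---|---|---|---|
| Adverse events | 8.1 | None; to 30 days after last dose, later if related | Maximum grade |
| Laboratory | 8.2 | None | Shift to worst on-study grade, unscheduled visits included |
| ECG | 8.4 | None | Listing with flagged values, scheduled or unscheduled |
| Vital signs | 8.3 | ICU admission | Nothing beyond each visit's minimum and maximum |

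Vital signs are the exception. SAP 4.4 imputes no missing data unless otherwise stated, so nothing restores the omitted period. Read literally, readings after return from ICU to the ward are also excluded.

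**2. Values lost per patient.** SAP 4.5 maps safety readings to the nearest visit and keeps one per visit, the closest to the target day. SAP Tables 2 to 4 define no vital-sign windows, so I assume the dosing-period visits in protocol Table 1. ICU admission on Day 4 with 10 further days runs to Day 14. The visits in that span are Days 5, 8, 10 and 12, so about 4 values per parameter are lost. A Day 14 reading mapped to the Day 15 visit would make a fifth.

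**3. Patients affected (assumed ICU rates).** Number truncated = N × rate, taking N = 247 as planned or 371 as the maximum after re-estimation (protocol 9.6), and assuming nearly all are treated.

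| Assumed ICU rate | N = 247 | N = 371 |
|---|---|---|
| 10% | 25 | 37 |
| 20% | 49 | 74 |
| 30% | 74 | 111 |
| 40% | 99 | 148 |

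**4. Difference hidden in mean change (assumed).** Let p be the share of an arm's readings at a visit that fall after ICU admission, and d the mean systolic change in those readings. Assume no mean change in the rest.

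- All readings: arm mean change = p × d + (1 − p) × 0 = p × d.
- Difference, selinexor minus placebo = (p_selinexor − p_placebo) × d.
- Truncated table: 0 − 0 = 0 in every case.

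| p placebo | p selinexor | d = −10 mmHg | d = −20 mmHg |
|---|---|---|---|
| 0.10 | 0.20 | −1 | −2 |
| 0.20 | 0.30 | −1 | −2 |
| 0.20 | 0.40 | −2 | −4 |
| 0.30 | 0.20 | +1 | +2 |

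An ICU excess of 10 to 20 points thus hides 1 to 4 mmHg. A 10-point reduction hides 1 to 2 mmHg in the other direction. The truncated difference is exactly zero only because the non-ICU change was set to zero in both arms.

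**The case against.** The strongest reply is that harm is captured elsewhere. Protocol 7.3.1 requires clinically relevant findings that meet the adverse-event definition to be recorded. The SAP reports adverse events, deaths, ICU admission, mechanical ventilation and PaO2:FiO2 by arm, and the stopping criteria in protocol 9.5 cover death and invasive ventilation. An excess of ICU admissions would show directly in its own endpoint. This limits the consequence but is not a complete backstop. Protocol 8.1.2 lets investigators treat a sign as part of the COVID-19 course and not report it as an adverse event, and low pressure, fever or desaturation in ICU are plausible candidates.

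It is also fair to say that ICU readings partly reflect supportive care, so pooling them can mask abnormality too. That argues for showing both tables.

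A third reply concerns blood pressure. The vital-signs footnote to protocol Table 1 names respiratory rate, temperature and oxygen saturation only. Blood pressure and pulse appear in protocol 7.3.1 and SAP 8.3, so twice-daily blood pressure is not clearly established. The mmHg figures depend on its being recorded in ICU; the truncation itself applies to every parameter.

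Some stronger readings are tempting but unsupported:

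- A reader might infer that only patients who never deteriorated remain. Readings before ICU admission, including the decline towards it, stay in, as do those of patients who worsen on the ward.
- Twice-daily collection over 10 days suggests 20 lost readings. SAP 4.5 keeps one per visit for every patient, so most would never have entered the table.
- One might calculate a share of hypotension cases lost. SAP 8.3 plans no incidence table.
- One might conclude that patients already in ICU at entry contribute nothing after baseline. Protocol 4.1 admits patients needing oxygen by various devices, "or high flow nasal canula in order to maintain" adequate saturation. Protocol 4.2 excludes critical illness, including "oxygen delivered by noninvasive positive pressure ventilation, or clinical diagnosis of respiratory failure in setting of resource limitations", but not ICU location as such. Nothing says such patients will enrol, and the SAP's qualifier about applicability is undefined. This remains an inference, although a rule is needed.

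**Conclusion.** The point holds as a safety-reporting gap of moderate weight. SAP 8.3 truncates the trial's only vital-sign summaries at a post-randomization outcome, and no other planned vital-sign output covers the readings left out. The between-arm tables are distorted if treatment affects ICU admission in either direction.

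The size is modest and conditional: about 4 values per parameter for the example patient, and about 1 to 4 mmHg hidden under the assumed ICU excess and systolic fall. The visit-based count assumes the protocol Table 1 visits; the ICU rates and pressure changes are assumptions, because the documents supply neither.

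A reader might go further and say that the trial's safety conclusions are biased towards showing no harm. The documents do not support that. The effect is confined to descriptive vital-sign tables, the other safety outputs have no ICU cut-off, and neither the primary endpoint nor any other hypothesis test depends on these tables.

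**What to change.** Amend SAP 8.3 as follows:

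- Make the main by-visit summary include all on-study vital-sign readings, ICU readings included.
- Add a summary from baseline to worst on-study value by arm, using all scheduled and unscheduled readings. The shift tables in SAP 8.2 rest on CTCAE laboratory ranges, so define worst for each vital sign, for example the lowest and highest value of blood pressure, pulse and temperature and the lowest oxygen saturation.
- Keep the version truncated at ICU admission as a labelled supplementary table, with the number of patients truncated at each visit in each arm.
- State how the truncated version treats patients already in ICU at first dose and readings after ICU discharge, and define the vital-sign analysis visits.

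The cost is SAP wording and one or two extra tables from data already scheduled for collection. The drawback is that ICU readings partly reflect supportive care; the supplementary table lets the reader see the comparison without them.
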